#### (Fasting Condition)

(done within 28 days prior to check in of period one), 2D echo and chest X-ray (done within 6 months prior to check in of period one).

Subjects were monitored for safety during the entire study. The subject's Clinical examination along with vital signs (seated blood pressure, radial pulse rate and oral/aural temperature) were measured during check-in and check-out of each period.

Clinical examination was done on prior to dosing on Day 06 in each study period. Oral/aural temperature was measured prior to dosing in each study period.

Vital parameters – seated blood pressure and radial pulse rate were measured at prior to dosing, 1.00, 3.00, 5.00 and 11.00 hours post dose in each period from Day 1 to Day 5, and from Day 6 to Day 9, vitals were measured prior to dosing, at 1.00, 2.00, 3.00, 5.00, 8.00 and 11.00 hours post dose in each period.

Note

- On Day 6 the Vital signs (i.e. up to 3.00 hours post dose) was performed at bed side.
- For subjects who were randomized to treatment A, the vitals were checked at 5.00 hours post dose during day 1 to Day 5.

ECG was performed at 1.00 and 3.00 hours post dose in each period on Day 6, before period II check-in for subject study eligibility and at check-out of each period of the study.

In each study period creatinine clearance and serum potassium levels were measured on Day 05 for the dosing eligibility of the subjects.

For the safety of the subjects, hematology (except blood grouping and Rh typing) and biochemistry (except random blood sugar) investigations were repeated at the end of the study.

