### Electrolyte and Metabolic Abnormalities

In addition to causing hyperkalemia, Spironolactone Oral Suspension can cause hyponatremia, hypomagnesemia, hypocalcemia, hypochloremic alkalosis, and hyperglycemia. Asymptomatic hyperuricemia can occur and rarely gout is precipitated. Monitor serum electrolytes, uric acid and blood glucose periodically. *Gynecomastia* 

Spironolactone Oral Suspension can cause gynecomastia. In RALES, patients with heart failure treated with a mean dose of 26 mg of spironolactone once daily, about 9% of the male subjects developed gynecomastia. The risk of gynecomastia increases in a dose-dependent manner with an onset that varies widely from 1-2 months to over a year. Gynecomastia is usually reversible.

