### Use in Patients with Electrolyte Disorders

In patients with hypokalemia or hypomagnesemia, toxicity may occur despite serum digoxin concentrations below 2.0 ng/mL, because potassium or magnesium depletion sensitizes the myocardium to digoxin. Therefore, it is desirable to maintain normal serum potassium and magnesium concentrations in patients being treated with digoxin. Deficiencies of these electrolytes may result from malnutrition, diarrhea, or prolonged vomiting, as well as the use of the following drugs or procedures: diuretics, amphotericin B, corticosteroids, antacids, dialysis, and mechanical suction of gastrointestinal secretions.

Hypercalcemia from any cause predisposes the patient to digitalis toxicity. Calcium, particularly when administered rapidly by the intravenous route, may produce serious arrhythmias in digitalized patients. On the other hand, hypocalcemia can nullify the effects of digoxin in humans; thus, digoxin may be ineffective until serum calcium is restored to normal. These interactions are related to the fact that digoxin affects contractility and excitability of the heart in a manner similar to that of calcium.

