#### 6.5 Blood Loss

The total blood loss per subject in the study will not exceed 292 mL for male/post-menopausal female subjects and 296 mL for female subjects of child bearing potential. In addition to the above, about 3-5 mL of blood will be collected for repeat post study safety assessment whenever needed or as decided by the Physician/Clinical Investigator/Principal Investigator.

	PK samples for two periods (50 samples of 5 mL each)	:	250 mL
+	Discarded heparin containing blood for two periods (40 x 0.5 mL)	;	20 mL
+	Blood withdrawn for screening	:	09 mL
+	Blood sample collection for Creatinine clearance and serum potassium for two periods (02 x 03 mL)	:	06 mL
+	Blood sample collection for post-study safety assessment	:	07 mL
	Total Blood Loss for male/post-menopausal female subjects		292 mL

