#### 6.7 Total duration of subject participation in the study

- Screening: Screening will take place within 28 days before the start of the study.
- Dosing: Day 1 to 9 in each period (Including a gap of at least 28 days between two successive treatment schedules of the study as wash out period)
- Follow up: Adverse event will be considered as related to the study if noticed or reported before study completion date and will be followed up till resolution.

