#### ECG Measurements:

- ECG will be performed before period II check in and subject study eligibility will be assessed as per the principal investigator discretion.
- ECG will be performed at 1.00 and 3.00 hours post dose in each period on Day 6 with a window period of ± 45 minutes from schedule time.
- ECG will be performed at check-out of each period of the study.

Note:

- On Day 6 the Vital sings (i.e. up to 3.00 hours post dose) will be performed at bed side only.
- 2D echo will be performed at the time of screening.
- Dosing will be done under the supervision of cardiologist.
- For subjects who are randomized to treatment A, the vitals will be checked at 5.00 hours post dose during day 1 to Day 5. However, the vitals time points

Page 55 of 83

Protocol for Drug-Drug Interaction Study of Spironolactone and Digoxin (Fasting Condition) Confidential

will be similar from day 6 for treatment groups A and B.

Vital signs may also be carried out at any time during the conduct of the study if the attending physician feels it necessary. In case of abnormality in vital signs during pre-dose vitals, recording, medical opinion will be taken whether to dose the subject or not.

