#### Additional Laboratory evaluations (Biochemistry):

In each study period creatinine clearance and serum potassium levels to be measured on day 05 and the dosing eligibility of the subjects will be done as per the principal investigator discretion.

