#### Appendix II: Assessment schedule

The following time-and-events table illustrates the planned schedule of assessments:

\*Chest X-Ray (P/A view) will be taken for the volunteer whose X-Ray was taken more than 6 months

VASAV: INSTITUTIONAL Period I.

	MONTE CONTRACT OF TOTAL	1
Bernin I	ETHICS COMMITTEE	[
Pictures.		P_SP
2010	APProtocol-No.;ED	-011
ž	METRUVEL	

Protocol for Drug-Drug Interaction Study of Spironolactone and Digoxin (Fasting Condition) Confidential

\* ECG will be performed at 1.00 and 3.00 hours post dose in each period of the study and before check in of period-II & before checkout of each period.

\$ Spironolactone Oral Suspension will be administered from Day 1 to Day 5 and Day 7 to Day 9, to the subjects who will be randomized to treatment B as per randomization scheme and treatment A or B will be administered on day 6.

The day prior to drug administration in each period for this protocol will be considered as Day '-1'.

The day of dosing in each period for this protocol will be considered as Day 1.

-  Post study (hematology and biochemistry) laboratory evaluations will be done at last blood sample collection of the study.
-  Serum pregnancy test will be done for female subjects with child bearing potential and Urine pregnancy test will be done for post-menopausal female subjects during screening, each period check-in (Day '-1').
-  Evaluation of inclusion/exclusion criteria will be carried out prior to check-in of period I of the study.
-  Investigational products (substrate) will be dispensed a day before dosing and perpetrator will be dispensed on the day of dosing in each period of the study.

Condition)	Confidential

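### Low-priority safety improvement: the Day 5 check before digoxin omits serum magnesium, so no Treatment B dose has a scheduled magnesium value between the start of spironolactone and digoxin

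*Protocol*

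**What the plan says.** **Dosing.** Protocol section 6.2 gives Treatment B subjects spironolactone suspension 100 mg daily on Days 1 to 5 and 7 to 9, and together with digoxin 250 mcg on Day 6.

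**The Day 5 check.** Section 11.2 reads: "creatinine clearance and serum potassium levels to be measured on day 05 and the dosing eligibility of the subjects will be done" at the principal investigator's discretion. The blood-loss table in section 6.5 describes the same sample: "Blood sample collection for Creatinine clearance and serum potassium for two periods (02 x 03 mL". The Day 5 row of Appendix II lists the same two tests. The study report, written after Amendment 01, agrees in section 9.5.1: "In each study period creatinine clearance and serum potassium levels were measured on Day 05 for the dosing eligibility of the subjects".

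**What the protocol says about magnesium.** Section 2.1.7 says the suspension "can cause hyponatremia, hypomagnesemia, hypocalcemia, hypochloremic alkalosis, and hyperglycemia" and advises periodic monitoring of serum electrolytes. Section 2.2.7 says "potassium or magnesium depletion sensitizes the myocardium to digoxin" and calls normal potassium and magnesium desirable during digoxin treatment.

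**When magnesium is measured.** It is in the section 11.2 screening panel. Section 6.7 sets the timing: "Screening will take place within 28 days before the start of the study". The biochemistry panel is then repeated once, under Appendix II: "Post study (hematology and biochemistry) laboratory evaluations will be done at last blood sample collection of the study".

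The SAP covers pharmacokinetic and statistical analysis and does not address this check.

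**The concern.** The Day 5 sample supports a decision: whether the subject may take digoxin the next day. The protocol's own background names potassium and magnesium together as the electrolytes whose depletion matters for digoxin, yet the check includes only potassium. In Treatment B the subject has by then taken five doses of a drug that the protocol says can lower magnesium.

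What is at stake is subject safety at one dose of a drug that section 11.2 calls narrow therapeutic index. No endpoint, estimate or confidence-interval rule is affected. Treatment A is outside the point, because no spironolactone is given in that period.

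Magnesium is not the only electrolyte linked to both drugs. Potassium is too, and is already checked. Calcium is too, but section 2.2.7 says that low calcium can nullify the effect of digoxin, which is not the sensitising effect at issue. The point is therefore limited to magnesium.

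**Working it through.** **1. The plan's own figure.** The only stated figure that the fix could change is total blood loss (section 6.5):

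50 × 5 + 40 × 0.5 + 9 + 2 × 3 + 7 = 250 + 20 + 9 + 6 + 7 = 292 mL.

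Adding 2 × 2 mL for pregnancy tests gives 296 mL. Both match the protocol.

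**2. Age of the last planned magnesium value at the Day 6 decision.** Inputs:
- Screening runs from Day −28 to Day −3 (Appendix II).
- Day −1 is the day before first dosing (Appendix II notes).
- Day 1 of Period I is 11 Mar 2019, and digoxin is given on 16 Mar and 13 Apr 2019 (report section 9.4.1).

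Day −28 to Day −3 is therefore 11 Feb to 8 Mar 2019.

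| Sequence | Subjects | Treatment B digoxin | Age of screening value |
|---|---|---|---|
| BA | 14 | 16 Mar | 8 to 33 days |
| AB | 14 | 13 Apr | 36 to 61 days |

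Counting 28 days back from check-in on 10 Mar instead moves the upper ends to 34 and 62 days. In every case the value predates any spironolactone.

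**3. Treatment B periods with magnesium scheduled between the first spironolactone dose and digoxin.** There are 14 + 14 = 28 Treatment B periods (report Table 9). Sections 11.2 and 6.5 and Appendix II schedule no magnesium on Days 1 to 6, so the count is 0 of 28.

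**4. What the end-of-study value adds.** The last sample was on 17 Apr 2019 (report synopsis).
- Sequence AB: this is Day 10 of the Treatment B period, four days after digoxin (13 to 17 Apr) and after nine daily spironolactone doses (8 to 16 Apr).
- Sequence BA: the last spironolactone dose was on 19 Mar, 29 days earlier, so the value says little about the Treatment B period.

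Protocol section 11.3 requires a clinically significant abnormal laboratory value that is a change from baseline to be recorded as an adverse event. Report section 12.2 records none. Together these imply 0 of 14 AB subjects with a magnesium change that the investigator judged clinically significant. The exact one-sided 95% upper bound on that rate is 1 − 0.05^(1/14) = 0.193, so 14 subjects leave rates up to about 19% open.

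**5. Precision cost of a withheld dose.** With one subject lost (14 + 14 becomes 13 + 14), the log-scale half-width is multiplied by

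t(0.95, 25)/t(0.95, 26) × √[(1/13 + 1/14)/(2/14)] = 1.7081/1.7056 × 1.0190 = 1.0206.

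The half-width with 28 subjects is t(0.95, 26) × √ln(1 + CV²) × √[½(1/14 + 1/14)], using the intra-subject CVs in report Table 11:
- AUC0-96, CV 18.56%: 0.0839, which agrees with ½ ln(91.59/77.45) = 0.0838. With 27 subjects it is 0.0856.
- Cmax, CV 40.07%: 0.1759, which agrees with ½ ln(77.02/54.18) = 0.1759. With 27 subjects it is 0.1795.

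**The case against.** The strongest case against is that this is a preference and not a flaw.

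- **Background text used outside its setting.** Section 2.1.7 lists low magnesium as something spironolactone can cause, without a rate or time course. Section 2.2.7 concerns patients under digoxin treatment with electrolyte disorders. Here, healthy adults aged 20 to 35 with a normal laboratory screen take one 250 mcg tablet per period. This stands as a limit on the size of the risk. It does not explain why the protocol checks one of the two electrolytes it names together and leaves out the other.
- **Other safeguards.** Section 11.2 states "Dosing will be done under the supervision of cardiologist". It also provides a Day 6 pre-dose examination, vital signs before dosing and six times after, ECGs at 1 and 3 hours, housing to 96 hours and emergency drugs on site, and it judges these measures sufficient. Section 7.2 excludes QT/QTc above 450 ms. This largely stands: these measures make serious harm unlikely. The ECGs and later vital signs come after the dose, however, and none of the safeguards gives the investigator a magnesium value when deciding whether to dose.
- **Reassuring outcome.** The 14 AB subjects had magnesium measured after nine doses, and no adverse event was recorded. This stands as the most direct evidence available. It was known only afterwards, rests on investigator judgement, and does not exclude milder lowering or a low value at dosing. The individual listings are not available here.

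A reader might infer that no magnesium value was ever taken under spironolactone. The AB end-of-study values show otherwise; the gap is confined to the time before the digoxin dose. A reader might also infer a protocol breach or harm to subjects. The documents support neither.

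**Conclusion.** The point holds as a cheap, low-priority safety improvement. In 0 of 28 Treatment B periods is magnesium scheduled after that period's spironolactone began and before digoxin. The value to hand is 8 to 33 days old in BA and 36 to 61 days old in AB.

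The documents give no frequency of low magnesium, so the number of subjects who might have been dosed with a low value cannot be derived. The absolute risk is low. The pharmacokinetic conclusions are untouched.

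The verdict rests on the protocol's own statements about both drugs, and on the screening window and dosing dates being followed as stated. The inference from the absence of adverse events also assumes that the section 11.3 recording rule was applied to the final panel.

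**What to change.** The trial is complete, so this applies to a repeat study or to reuse of the protocol.

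- **Section 11.2:** make the Day 5 tests creatinine clearance, serum potassium and serum magnesium, run on the sample already drawn.
- **Section 6.5 and the Day 5 row of Appendix II:** update to match.
- **Decision rule:** the investigator and supervising cardiologist review any magnesium value below the laboratory's reference range, and record the decision to dose or withhold before Day 6 dosing.

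**Cost.** The safety reason needs 28 assays (Treatment B only). Testing everyone takes 28 × 2 = 56 and is simpler to run, because the Day 5 check already applies to all subjects. Magnesium is already in the study panel, and no visit or procedure is added. If the 3 mL sample is enough, blood loss stays at 292 mL (296 mL for women of child-bearing potential). If an assumed 1 to 3 mL more per period is needed, it becomes 294 to 298 mL (298 to 302 mL). The laboratory should confirm the volume.

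**Downside.** A withheld Treatment B dose loses a paired subject: dosed subjects are not replaced (section 7.5.3), and the intervals use only subjects who completed both periods (report section 11.4.2.2). The first such loss widens the 90% intervals by about 2% on the log scale, which is acceptable for a safety decision.

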#### Risk evaluation and mitigation strategy:

Since healthy subjects are being enrolled in the study, there is no benefit to them. In general, the adverse reactions of digoxin are dose-dependent and occur at doses higher than those needed to achieve a therapeutic effect. Hence, adverse reactions are less common when digoxin is used within the recommended dose range or therapeutic serum concentration range and when there is careful attention to concurrent medications and conditions.

As Digoxin is a narrow therapeutic index drug, the drug administration will be done under the supervision of a cardiologist along with a continuous close monitoring by medical and para medical personnel. Since most of the digoxin is excreted unchanged in the urine, subjects with significant difference from normal serum creatinine or creatinine clearance values will not be considered for this study. In addition, only the subjects with normal 2D echo and QTc interval will be enrolled into the study.

Considering the single dose nature of this study and 28 days washout period between dosing periods, the effects caused by 250 mcg Tablet of Digoxin are not expected to impact on safety in the healthy volunteer population. Even if adverse events are observed, they are likely to be benign, transient, not require intervention. Nevertheless, close monitoring of blood pressure, pulse rate, and ECG will be conducted during the time maximum pharmacodynamic effects are observed (i.e. during 1 - 3 hours post dose).

Furthermore, subjects will be domiciled until day 04 (i.e. until 96 hours after drug

Protocol for Drug-Drug Interaction Study of Spironolactone and Digoxin (Fasting Condition) Confidential

administration in each period), thus providing an optimal setting for the clinical monitoring and, if necessary, management of any adverse events. However, subjects will only be allowed to leave the clinical center after clinical examination, ECG, and other safety measures are repeated at the end of study visit.

KCl Injection, KCl oral Syrup, Amiodarone Injection 150 mg, Xylocard Injection will be made available in the ICU at the time of study as a precautionary measure. Overall, based on the known AE profile of 250 mcg Tablet of Digoxin, strict screening, inclusion and exclusion criteria, routine safety assessments and planned close monitoring of known AE's, blood pressure, pulse rate, ECG, and 28 days washout period is considered sufficient to mitigate any potential risk to the subjects.

Blood tests:		Urine analysis
Hematology	Biochemistry	Office analysis
Hemoglobin	Random blood glucose	Physical Examination
Total RBC Count	Blood urea	Chemical Examination
Total WBC Count	Serum creatinine	Microscopic examination
Platelet count	Serum uric acid	
Differential count	Serum sodium	
Peripheral smear	Serum potassium	
Blood group	Serum chloride	
ESR	Serum calcium	
	Serum magnesium	
Serology:	Liver Function Tests:	
HIV (1 & 2)	Total Bilirubin	
antibodies	Direct Bilirubin	
HBsAg (Hepatitis	SGOT (AST)	
Bsurface antigen)	SGPT (ALT)	
Anti-hepatitis C	Alkaline phosphatase	
Virus (HCV)	Total proteins	
VDRL (RPR)	Albumin	
	Total Cholesterol	

Laboratory evaluations performed during screening are as follows:

Note: The laboratory parameters will be evaluated as per laboratory reference ranges (Appendix-IV). In rare instances, when the values are out of laboratory

Protocol for Drug-Drug Interaction Study of Spironolactone and Digoxin (Fasting Condition) Confidential

reference ranges, then those values will be correlated with clinical condition of the subject for further evaluation.

Laboratory (safety) evaluations performed at the end of study:

About 07 mL of blood will be collected from each subject for safety evaluation [which includes hematology (except blood group and Rh typing) and biochemistry (except random blood sugar) as per section 11.2] at the end of the study. If the subject does not come for the safety evaluation on scheduled time for any reason, follow-up will be done as per applicable Clinsync SOP.

#### 11.3 Handling and reporting of Adverse Events and Serious Adverse Events Definitions

An adverse event (AE) is any untoward medical occurrence in a patient or clinical investigation subject administered a pharmaceutical product and that does not necessarily have a causal relationship with this treatment. An AE can therefore be any unfavorable and unintended sign (including an abnormal laboratory finding), symptom, or disease temporarily associated with the use of a medicinal (investigational) product whether or not related to the medicinal (investigational) product.

[figure not shown]
Adverse Drug Reaction (ADR): A response to a drug which is noxious and unintended and which occurs at doses normally used in man for prophylaxis, diagnosis, or therapy of disease or for modification of physiological function.

**Unexpected Adverse Drug Reaction**: An adverse reaction, the nature or severity of which is not consistent with the applicable product information of Carospir® Spironolactone Oral Suspension, 25 mg/5 mL.

Serious Adverse Event (SAE): A serious adverse event (experience) or reaction is any untoward medical occurrence that at any dose

- Results in death,
- Is life-threatening,
- Requires inpatient hospitalization or causes prolongation of existing hospitalization,
- Results in persistent or significant disability/incapacity,

Congenital anomaly/birth defect,

Protocol for Drug-Drug Interaction Study of Spironolactone and Digoxin (Fasting Condition) Confidential

• Requires intervention to prevent permanent impairment or damage

Note: The term "life threatening" in the definition of "serious adverse event" refers to an event in which the subject was at risk of death at the time of the event; it does not refer to an event, which hypothetically might have caused death if it was more severe.

TERM	DESCRIPTION COMMENT
Certain/	A clinical event, including It is recognized that this stringent
Definite	laboratory test abnormality, definition will lead to very few
	occurring in a plausible time reports meeting the criteria, but this
	relationship to drug is useful because of the special value
	administration, and which cannot of such reports. It is considered that
	be explained by concurrent time relationships between drug
	disease or other drugs or administration and the onset and
	chemicals. The response to course of the adverse event are
	withdrawal of the drug important in causality analysis. So
	(dechallenge) should be also is the consideration of
	clinically plausible. The event confounding features, but due weight
	must be definitive must be placed on the known
	pharmacologically or pharmacological and other
	phenomenologically, using a characteristics of the drug product
	satisfactory rechallenge being considered. Sometimes the
	procedure if necessary. clinical phenomena described will
	also be sufficiently specific to allow
	a confident causality assessment in
	the absence of confounding features
	and with appropriate time
	relationships, e.g. penicillin
	anaphylaxis.
Probable/	A clinical event, including This definition has less stringent
Likely	laboratory test abnormality, with wording than for "certain" and does
VASAVI INSTITUTIONAL	-CMP-SPI-001; Version 02; Date: 07 Aug 2018 Page 59 of 83
APPROVED	$C_{111} = 0.1 \times 0.017, Totoloh = 0.27, Duto. 07 Aug 2010 Tug 201$

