#### Cardiac

Therapeutic doses of digoxin may cause heart block in patients with pre-existing sinoatrial or AV conduction disorders; heart block can be avoided by adjusting the dose of digoxin. Prophylactic use of a cardiac pacemaker may be considered if the risk of heart block is considered unacceptable. High doses of digoxin may produce a variety of rhythm disturbances, such as first-degree, second-degree (Wenckebach), or third-degree heart block (including asystole); atrial tachycardia with block; AV dissociation; accelerated junctional (nodal) rhythm; unifocal or multiform ventricular premature contractions (especially bigeminy or trigeminy); ventricular tachycardia; and ventricular fibrillation.

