#### CNS

Digoxin can produce visual disturbances (blurred or yellow vision), headache, weakness, dizziness, apathy, confusion, and mental disturbances (such as anxiety, depression, delirium, and hallucination).

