### 4.2 Randomization

The order of receiving the treatment A and treatment B for each subject during the study will be determined randomly. According to the randomization schedule, subjects will receive the assigned formulation in each period, with the possible sequences 'AB' or 'BA' (where A = substrate and B = substrate & perpetrator). Equal allocation of subjects to each sequence will be ensured. The randomization will be balanced and the randomization schedule as well as the dispensing records will be kept in the drug store under controlled access. The study personnel involved in dispensing (pharmacist) and the Principal Investigator will be accountable for ensuring compliance to randomization schedule. Randomization schedule will be generated using SAS® software 9.3 or higher.

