### 6 TREATMENT OF SUBJECTS

### 6.1 Treatments to be administered

Treatment A		
Name of the Product	:	LANOXIN ® (digoxin) USP 250 mcg
Dose	:	250 mcg
Dosing Schedule	:	One tablet as a single dose to each subject
Route/Mode of Administration	;	Orally with $240 \pm 2 \text{ mL}$ of water
Treatment Period	:	Single dose for 1 Day (day 6) as per randomization schedule
Treatment B		
Name of the Product		LANOXIN ® (digoxin) USP 250 mcg + Spironolactone Oral Suspension 100 mg (CaroSpir ® Oral Suspension 20 mL of 25
		mg / 5 mL)
Dose		250 mcg of digoxin and 100 mg of spironolactone as 20 mL of 25 mg / 5 mL
VASAVI INSTITUTIONAL ETHICS COMMITTEE	k 	

C-CMP-SPI-001; Version 02; Date: 07 Aug 2018

Protocol for Drug-Drug Interaction Study of Spironolactone and Digoxin (Fasting Condition) Confidential

Dosing Schedule		One tablet of digoxin and 20 mL of 25mg/5mL CaroSpir oral suspension as a single dose to each subject
Route/Mode of Administration	:	Orally with about $240 \pm 2$ mL of water
Treatment Period	:	Single dose for 9 Days as per randomization schedule

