#### **Recording of Adverse events**

All adverse events including both observed and volunteered ones will be recorded on the appropriate AE form (As per applicable Clinsync SOP), irrespective of its association with the investigational products. Laboratory parameters, which are outside the clinically acceptable ranges but are not clinically significant as per PI discretion, must be recorded in the lab report and respective CRF page as Nil Significant. Clinically significant abnormal laboratory values that represent a change from baseline should be recorded diagnostically as AE's (e.g.: for elevated serum glucose, the AE would be described diagnostically as "hyperglycemia"). Determination of Clinical significance is based on the Investigator's medical judgment/discretion. PI shall evaluate the event for its severity, causality and seriousness that require immediate report to IEC and sponsor.

The institutional ethics committee (IEC), regulatory agency (ies), and the sponsor will be informed regarding the adverse events as necessary. Any serious adverse events will be recorded in appropriate Serious Adverse Event Reporting Form (As per applicable Clinsync SOP).

The investigator shall report all serious and unexpected adverse events to the licensing authority, the sponsor or his representative, whosever had obtained permission from the licensing authority for the conduct of the study and the ethics committee that accorded approval to the study protocol, within twenty-four hours of their occurrence. In case the Investigator fails to report any serious adverse event within the stipulated period, he shall have to furnish the reason for the delay

Protocol for Drug-Drug Interaction Study of Spironolactone and Digoxin (Fasting Condition) Confidential

to the satisfaction of the Licensing Authority along with the report of the serious adverse event. The report of the serious adverse event, after due analysis shall be forwarded by the investigator to the Licensing Authority, chairman of the Ethics Committee and the Head of the Institution where the trial has been conducted within fourteen calendar days of the occurrence of the serious adverse event.

Serious adverse events report submitted to Licensing Authority will be in color coded binding, where the reports of SAEs of Deaths are submitted in red cover, the report of SAEs of injury other than deaths in blue cover and the remaining cases of SAE report in white cover.

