Each adverse event will be evaluated for duration, severity, and action taken, outcome and association with the study medication. The study may be suspended or terminated depending upon the seriousness of the adverse events.

Note: The reporting of all serious, unexpected suspected adverse reactions, any unexpected fatal or life-threatening suspected adverse reactions and any findings from the clinical study will be submitted as a per the timelines mentioned in 21 CFR 312.32 and 21 CFR 312.33 and compliance with the FDCA (21 U.S.C. §§ 301 et. seq.).

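### Expectedness is judged only against the Carospir product information, although digoxin is also an investigational product and the only drug in Treatment A

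*Protocol*

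**What the plan says.** Under the definitions in protocol Section 11.3, a reaction is unexpected if it is one "the nature or severity of which is not consistent with the applicable product information of Carospir". Only that product is named.

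Two reporting sentences later in Section 11.3, under the recording of adverse events, use the term. One reads "The investigator shall report all serious and unexpected adverse events to the licensing authority" and sets a 24-hour limit. The other is a closing note that begins "The reporting of all serious, unexpected suspected adverse reactions" and ties such reports to the timelines in 21 CFR 312.32 and 312.33.

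Section 4.2 gives the content of the two treatments: "where A = substrate and B = substrate & perpetrator". Section 6.1 gives the Treatment A schedule: "Single dose for 1 Day (day 6) as per randomization schedule". Section 5 lists both treatments under investigational products, and Section 5.1.1 covers the supply of both drugs under that heading. The LANOXIN prescribing information is in the reference list (Section 18), but nothing in the text available makes it a reference for expectedness. The SAP covers only pharmacokinetic and statistical analysis and has no adverse event definitions.

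**The concern.** Expectedness is a statement about a particular product: is this reaction already described for the drug thought to have caused it? In a Treatment A period the drug that can be suspected is digoxin, and for a subject in sequence AB in Period I no spironolactone has yet been given in the study. Applied as written, the rule compares that subject's reaction with information on a drug not received.

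The protocol's own safety reasoning makes the omission stand out. The risk evaluation in Section 11.2 describes digoxin as having a narrow therapeutic index and builds the monitoring around its effects. Section 3.2 gives the purpose of the study as finding out whether spironolactone raises digoxin levels.

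At stake is the class given to a serious suspected reaction, and so whether it enters the regulatory route that depends on that class.

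**Working it through.** No arithmetic applies. The check sets the definition beside the dosing schedule, the protocol's two adverse-effect summaries and the reporting sentences.

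**Step 1: what has been received, and when** (Sections 4.2, 6.1 and 6.2)

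| Sequence and period | Days 1–5 | Day 6 | Days 7–9 |
|---|---|---|---|
| AB, Period I | nothing | digoxin | nothing |
| AB, Period II | spironolactone | both | spironolactone |
| BA, Period I | spironolactone | both | spironolactone |
| BA, Period II | nothing | digoxin | nothing |

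An AB subject in Period I has had digoxin only. A BA subject on Days 1–5 of Period I has had spironolactone only, and no digoxin at all. The treatment letter therefore does not show which products can be suspected on a given day.

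**Step 2: the two summaries** (Section 2.1.6 for spironolactone, Section 2.2.6 for digoxin)

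- Listed for spironolactone only: for example hyperkalemia, and leukopenia including agranulocytosis.
- Listed for digoxin only: for example the sentence beginning "Digoxin can produce visual disturbances (blurred or yellow vision".
- Listed for both: nausea, vomiting, diarrhea, headache, dizziness, confusion, gynecomastia and thrombocytopenia.

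**Step 3: class of a suspected reaction to digoxin alone**

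| Reaction | Rule as written (Carospir) | Judged against digoxin |
|---|---|---|
| Hyperkalemia | expected | unexpected |
| Agranulocytosis | expected | unexpected |
| Visual disturbances | unexpected | expected |
| Reactions on both lists | expected | expected |

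The class changes in the first three rows. In the last row it does not change by nature, although severity could still alter it.

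**Step 4: which reporting wording depends on the class** (Section 11.3)

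- The closing note on serious, unexpected, suspected reactions depends on it directly. The regulation is cited there for timelines, and no other reference for expectedness is named.
- The 24-hour sentence says serious and unexpected, but the next sentence speaks of any serious adverse event.
- The investigator's evaluation for immediate report to the ethics committee and sponsor uses severity, causality and seriousness, not expectedness.
- The fourteen-day report to the licensing authority, the ethics committee chairman and the head of the institution refers to the serious adverse event, with no separate condition on expectedness.
- All adverse events are recorded whatever their association with the products.

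The definition therefore certainly governs the closing note, possibly governs the 24-hour duty, and does not visibly govern the rest.

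**The case against.** The strongest reply is that the harmful direction, a reaction wrongly called expected, is largely covered elsewhere. A reader might infer that a serious hyperkalemia after digoxin alone would go unreported. The documents do not support that. The ethics committee and sponsor are told on grounds of seriousness, and the fourteen-day report carries no separate condition on expectedness. The sentence that begins "In case the Investigator fails to report any serious adverse event within the stipulated period" also points to a duty covering every serious event. This stands, and it limits the consequence. It does not repair the closing note, and the 24-hour sentence remains ambiguous.

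A reader might also take heart block as the leading example of a known digoxin effect wrongly called unexpected. That is weak. Section 2.2.6 says "High doses of digoxin may produce a variety of rhythm disturbances", and otherwise links heart block to pre-existing conduction disorders; Section 2.2.7 does the same for advanced or complete block. Subjects here are healthy, must have no clinically significant ECG abnormality, and take one 250 mcg tablet per period. Since the definition turns on severity as well as nature, serious block in such a subject may be unexpected against either product. An error in this direction would in any case add reports and withhold none.

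Two further limits stand. The definition refers to the product information, while the check uses the protocol's summaries because neither full label is available. Most of Amendment 01 is also not available. The one change that can be read concerns sample storage, so a correction to this definition cannot be ruled out, though nothing suggests one.

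**Conclusion.** The definition uses the wrong reference for digoxin and should be corrected. This is a rule that gives the wrong class when applied as written; it is not merely a missing detail.

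Its reach is small. It affects only reactions that are serious, suspected, and listed for one product and not the other. A reader might count 28 of 56 subject-periods as affected, since 28 subjects × 2 periods = 56 and each subject has one Treatment A period. That figure measures exposure to digoxin alone, not misclassification; many reactions are on both lists and keep their class. Nor do digoxin reactions in general change class.

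The study report records no adverse events (Sections 12.2 and 12.6), so no report was misfiled. Sample size, error rates and the pharmacokinetic comparison are untouched.

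The conclusion assumes that the protocol's adverse-effect summaries reflect the labels on the examples used, and that the unavailable amendment pages left the definition unchanged.

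**What to change.** Define an unexpected reaction as one not consistent with the product information of the investigational product suspected of causing it, among those the subject had actually received by its onset: LANOXIN for digoxin, Carospir for spironolactone. Where both are suspected, class the reaction as unexpected if it is inconsistent with either product's information.

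The rule should follow the product suspected and received, not the treatment letter. Assigning both labels to the whole of Treatment B would repeat the fault on Days 1–5 of Period I for BA subjects, who have not yet had digoxin. Receipt alone is also not enough: a BA subject in Period II has already had spironolactone in Period I, so the judgement of suspicion is needed as well.

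The 24-hour wording in Section 11.3 should be reconciled at the same time, so that it is clear whether the duty covers all serious events or only unexpected ones.

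The cost is a short change of wording. The LANOXIN information is already in the reference list. The either-product rule will produce some extra reporting in Treatment B: a suspected hyperkalemia attributed to both drugs would count as unexpected because it is not described for digoxin. As the study is complete, the change belongs in any reuse of this protocol text.
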